## **Analysis**

The analysis will focus on the proposed mediating factors (self-compassion and psychological flexibility) and how they explain the outcome of the CFT-incorporated group intervention. In order to study the processes of change, this study will measure change in mediators and outcomes over the course of the group.

In a mediation model, the effect of the independent variable (IV; CFT group) on a dependent variable (DV; outcome/change in symptoms) is conveyed through a third mediating variable. In order to be a mediator, a variable must change during the intervention, be associated with the intervention, and have an impact on the outcome.

In this study, it is hypothesised that self-compassion and/or psychological flexibility are the mediating variables that explain the influence of the group intervention on eventual outcome, i.e. the overall change in symptoms at the end of the group. Linear regression and nonparametric bias-corrected bootstrap, which corrects for skew in the data, will be applied to the data using SPSS, using the PROCESS macro. An effect of mediation will be indicated if the confidence interval does not contain zero.

Missing data will be handled using either the maximum likelihood or multiple imputation method, as recommended in literature.

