#### Rationale

There is a need for evidence-based answers to explain why and how psychological interventions are successful (Kazdin, 2007). Multimodal treatments are becoming the norm and breaking down these components to examine individual efficacies is not a good use of resources (Wicksell et al., 2010). CFT offers a complementary approach to be used alongside current interventions, targeting the inevitable feelings of shame and self-criticism in the process of adjusting to chronic pain. A strong correlation between self-compassion and psychological flexibility has already been established, and gaining insight into the direction of the relationship between these concepts and treatment outcome would be the next logical step. By focusing on mechanisms of change, better theories can be developed and may promote treatment efficacy (e.g. by matching to patient need). This would be a far more efficient way to develop interventions, whilst maintaining a person-centred delivery of care.

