## **Principal Research Question**

 Do self-compassion and psychological flexibility mediate change in a Compassion-Focused Therapy group for adults with chronic pain?

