# **Secondary Research Questions**

- Which is the better predictor of change - self-compassion or psychological flexibility?

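### No mediation model or role for the week-5 scores is specified; if change is taken over the same 11 weeks, an interval excluding zero cannot show direction, and the week-5 pain schedule is inconsistent

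*Combined protocol and SAP*

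**What the plan says.** The principal question is "Do self-compassion and psychological flexibility mediate change in a Compassion-Focused Therapy group for adults with chronic pain". The secondary question is "Which is the better predictor of change", asked of self-compassion against psychological flexibility. The Rationale states that "gaining insight into the direction of the relationship between these concepts and treatment outcome would be the next logical step", and the background on psychological flexibility acknowledges that cross-sectional work cannot tell whether process moved outcome or outcome moved process.

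The Analysis section says that "this study will measure change in mediators and outcomes over the course of the group" and describes the outcome as "the overall change in symptoms at the end of the group". A mediator must change during the intervention, "be associated with the intervention, and have an impact on the outcome". The method is "Linear regression and nonparametric bias-corrected bootstrap, which corrects for skew in the data", run with the PROCESS macro. The decision rule is: "An effect of mediation will be indicated if the confidence interval does not contain zero". No regression equation, outcome list, lag or reverse model is given, and week 5 is not mentioned.

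Procedure and Data Collection schedule week-5 scores. Design says that all five measures are taken at pre-, mid- and post-group. Data Collection limits week 5 to the starred questionnaires. The headings for anxiety and depression (HADS), wellbeing (SWEMWBS), self-compassion (SCS-SF) and psychological flexibility (MPFI-SF) carry a star; the Pain heading (BPI-SF) does not.

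**The concern.** A mediation claim is a claim about order and cause, and the plan's own definition requires the mediator to act on the outcome. The decision rule tests only whether an interval excludes zero. If both variables are measured as start-to-week-11 change, people who improve will tend to improve on both, and the interval can exclude zero whichever variable moved first, or if neither moved the other. With no comparison group, nothing else in the design removes shared improvement. The study could then report as a mechanism the ambiguity its background hoped to reduce.

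The week-5 scores could partly address this, but no use of them is prespecified in the sections available, so the choice of window could be made after the data are seen. The schedule conflict decides whether pain can enter a time-ordered analysis at all.

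**Working it through.** **1. The plan's own figure.** Sample Size gives 53-71 for power .8, citing r of 0.33 to 0.55 for the first path and absolute r of 0.47 to 0.66 for the second. Simulating a 95% bias-corrected bootstrap of the product of paths (800 studies, 800 resamples, unit residual variance):
- N = 71, a = 0.33, b = 0.47/0.58/0.66: power 0.78/0.81/0.83.
- N = 53, a = 0.39, b = 0.58/0.66: power 0.80/0.81. With a = 0.33, about 0.70.

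The range is consistent with its inputs. It was sized for a generic mediated effect, not for a lagged model.

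**2. Same-window rule.** The group variable is constant in a one-group design, so the indirect effect was taken as mean mediator change multiplied by the slope of outcome change on mediator change. The confidence level is not stated; 95% is assumed. N = 53 and 71. Share of studies in which the interval excludes zero:

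| Set-up | Mediator drives outcome | Outcome drives mediator | Shared improvement only |
|---|---|---|---|
| A | 87-100% | 38-93% | 87-100% |
| B | 37-100% | 42-100% | 67-99% |
| C | 27-66% | 24-73% | 98-100% |

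- A: no measurement error; r = 0.47 to 0.66 (0.66 at N = 53 only); mean change 0.3 or 0.5 SD per half; effects partly immediate, partly delayed; shared cause drawn afresh in each half.
- B: reliabilities .80 for the mediator (the lower bound quoted for the self-compassion subscales) and .94 for the outcome (HADS); effect r = 0.33 and 0.60; half-period change SD 1.0 or 0.5; a person-level factor explaining 20%, 30% or 50% of change.
- C: as B, with change SD 1.0, a 50% factor and effects delayed by one half.

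Absolute rates move with the assumptions. In every set-up the rule fires often under all three explanations.

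**3. Time-ordered model.** Week-11 outcome on pre-to-week-5 mediator change, adjusted for week-5 outcome, baseline outcome and baseline mediator, with B's reliabilities:
- Delayed forward effect: detected in 45-99% (change SD 1.0), about 23-69% (SD 0.5).
- Delayed reverse effect: significant in 4-5%.
- Forward effect acting within the same half: significant in 5-7%, mirror model 6-15%. A null lagged result is therefore uninformative.
- Shared improvement only, 50% person-level factor: significant in about 33-65%, mirror model about 55-86%.

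A similar lagged model under A gave only 6-10% for a shared cause, because there the cause does not persist from one half to the next.

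**4. Reading direction from significance patterns.** Under shared improvement only, taking one model significant and the other not as a direction gives a false reverse direction in 30-42% and a false forward one in 10-16% (reliabilities .80/.94). With .80/.83, using the SWEMWBS figure, these become 23-28% and 19-24%.

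**5. Power of the lagged model.** Fisher z with three covariates: detectable partial r = tanh(2.80/√(N − 6)).
- N = 53: tanh(2.80/√47) = 0.387.
- N = 71: tanh(2.80/√65) = 0.334.
- At a partial r of 0.20 (z = 0.2027), power is 28% and 37%; 80% power needs (2.80/0.2027)² + 6 = 197.

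**6. Multiplicity.** If the outcomes are HADS anxiety, HADS depression and SWEMWBS (an assumption), 3 outcomes × 2 mediators × 2 directions = 12 tests. If independent, 1 − 0.95^12 = 0.46.

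**The case against.** The strongest reply is that the plan never commits to a same-window model. The single phrase on change can cover all three occasions, both mediator scales are starred for week 5, and the outcome sits at the end of the group, so an ordered analysis fits the text. That stands: the simulated same-window model is a reading, and the defect is that no window or model is fixed.

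Next, direction is not a listed research question, and asking which construct predicts better needs no directional claim. The background's warning also concerns cross-sectional studies, whereas this study measures change. That stands too, but asking whether constructs mediate change, and requiring them to affect the outcome, still implies direction.

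Third, the lagged model can mislead. It does: under a persistent common cause it is often significant with no mediator effect. This limits what the remedy can claim; it does not rescue the decision rule.

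Finally, the Design sentence may be a loose summary and Data Collection the specific schedule. That is plausible, but the two still disagree.

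**Conclusion.** The point holds as under-specification combined with a decision rule that claims too much. If change is taken over the same 11 weeks, an interval excluding zero does not separate forward, reverse and shared change. The text establishes this; the rates are illustrations under assumed effects, lags, loadings and reliabilities (the documents give no reliability figure for the MPFI-SF), not error rates of the written plan.

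A reader might infer more in three ways, none supported:
- That the plan prescribes a same-window analysis and rules out an ordered one. It prescribes neither.
- That reverse causation explains a positive result just as well as mediation. Set-up A gives 38-93% against 87-100%; only its shared-cause case matches the forward case.
- That using week 5 would settle direction. It guards against delayed reverse causation, at about 5% false signals, but leaves about 33-65% under a 50% person-level common factor.

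The statement that week 5 has no role applies to the sections available for review. The pain schedule conflict is real, but separate and minor.

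**What to change.** 1. In the Analysis section, write the model and state the window of each mediator and outcome. Replace the decision rule so that an interval excluding zero in a pre-post change model is reported as association consistent with mediation, not as evidence of mechanism or direction.
2. As an exploratory supportive analysis for HADS, SWEMWBS, SCS-SF and MPFI-SF, prespecify the adjusted week-11 regression described above, with its mirror (mediator and outcome exchanged). Report both estimates with intervals and declare no direction from them.
3. State that time order helps against delayed reverse causation but not against a common cause, giving the simulated rates and their assumptions, and that a null lagged result is not evidence against mediation.
4. Reconcile Design with Data Collection and the Pain heading on whether the BPI-SF is completed at week 5. If it is not, state that the time-ordered analyses exclude pain.

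Cost: wording, one schedule correction and ordinary linear regressions, a method already named. No new data are needed for the four starred scales, though the missing-data method must also cover week-5 scores. The downside is several added exploratory tests that N = 53-71 was not sized for: 80% power needs a partial r of about 0.39 or 0.33.

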## Methodology

# **Participants**

Participants will be adults with chronic pain who attend and complete the CFT-incorporated groups at the Lothian Chronic Pain Service / Pain Management Programme.

Inclusion Criteria	Exclusion Criteria
- Chronic Pain lasting a minimum of 3	- Active substance misuse
months	
 
Active suicidality
 

 
Fluency of English sufficient for
 
	- Terminal illness
participation in the group and	
 
Inability to provide informed
 

completion of questionnaires	consent (as defined by the Five
- Aged 18+ (no upper age limit)	Statutory Principles of the Mental

- Ability to provide informed consent	Capacity Act, Code of Practice,
as judged by the clinical team	2007)

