# Design

This study will follow a within-group (non-randomised) effectiveness-implementation design (Curran, 2012). Five self-report measures will be completed by participants at three specified time periods (pre-, mid- and post-group; see *Procedure* below).

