#### **Procedure**

Potential participants will be identified through their initial assessment upon referral to the Chronic Pain Service. Those who are deemed to be suitable for a Pain Management Programme (e.g. capacity, motivation) will be offered an introductory group session, followed by invitation to an upcoming 11-week group. Information sheets and consent forms will be given out at the start of the group (week 1), to be completed and returned the following week. The information sheets will contain details about the purpose of the research, expectations of the participant in taking part and further information about consent, potential benefits, confidentiality and details of the researchers. Participants will be given time to consider the information and direct questions to the clinical team, to go home and consider the information privately, and also given the opportunity to phone the service and ask further questions if desired. Those who can provide written informed consent will complete pre-group measures at the start of week 1. Mid-group measures will be completed at the end of week 5 and post-group measures will be completed at the end of week 11. (See section 6.4 for details of outcome measures.) The clinical team will be available if participants require support to complete the measures (e.g. literacy issues). The data for participants who do not complete the group will not be used in the final analysis.

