### Intervention

All groups will follow the same 11-week, structured timetable, using Compassion-Focused Therapy. As there are no current guidelines for using CFT in chronic pain, exercises have been adapted from 'Compassion Focused Therapy for Dummies' (Welford, 2016), incorporating the key elements of CFT (Gilbert, 2009).

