#### **Data Collection**

Demographic information routinely collected by the service will be used for descriptive statistics (gender, age, area of residence, pain diagnoses and other relevant physical health conditions, duration of pain, employment status and recent pain-related contact with healthcare services).

The following self-report measures will be completed by participants at the beginning of week 1 (start) and at the end of week 11 (end). Questionnaires denoted with '\*' will be completed by participants at these time intervals and, additionally, at week 5 (mid-point).

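### The mediation analysis names the CFT group as its independent variable, but everyone analysed receives CFT; the indirect effect is undefined until a within-person model is written.

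*Combined protocol and SAP*

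**What the plan says.** The principal question is: "Do self-compassion and psychological flexibility mediate change in a Compassion-Focused Therapy group for adults with chronic pain". The Analysis section answers it with a mediation model in which "the effect of the independent variable (IV; CFT group) on a dependent variable (DV; outcome/change in symptoms) is conveyed through a third mediating variable". It sets three conditions for a mediator: it changes during the intervention, it is associated with the intervention, and it affects the outcome. Estimation is by linear regression with a bias-corrected bootstrap in the PROCESS macro. Mediation is declared if the confidence interval excludes zero; no confidence level is given.

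Four sections fix who is analysed and what they receive:

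- Participants: "Participants will be adults with chronic pain who attend and complete the CFT-incorporated groups".
- Intervention: "All groups will follow the same 11-week, structured timetable, using Compassion-Focused Therapy".
- Design: "This study will follow a within-group (non-randomised) effectiveness-implementation design".
- Procedure: "The data for participants who do not complete the group will not be used in the final analysis".

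Measures are taken at weeks 1 and 11. Under Data Collection, the starred questionnaires "will be completed by participants at these time intervals and, additionally, at week 5 (mid-point". The two mediator scales, the HADS and the SWEMWBS are starred; the BPI-SF is not.

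The Sample Size section cites a published guideline for 0.80 power and arrives at 53–71. It uses correlations of 0.33 to 0.55, which it reads as showing that a group intervention was related to psychological flexibility, and correlations of 0.47 to 0.66 in absolute value between acceptance and outcomes.

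**The concern.** An indirect effect in this framework is the product of the path from the IV to the mediator (a) and the path from the mediator to the outcome (b). The a path needs an IV that varies. There is no comparison arm, non-completers are excluded and the timetable is the same for all, so the named IV does not vary.

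What is at stake is the only decision rule for the principal question. As written, it refers to an interval for a quantity that this design does not define. The team would have to choose the model at the time of analysis, including which waves to use, which covariates to adjust for and which outcome to take. The sample-size argument is affected too, because one of its two inputs is an intervention-mediator correlation that a single-arm cohort cannot produce.

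**Working it through.** **1. The plan's own sample size.** The 53–71 is read from a guideline that the document does not reproduce, and no exact pair of path values is stated, so an exact reproduction is not possible. A simulation with an IV that varies between people, unit residuals and a bias-corrected bootstrap 95% interval gives:

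- n = 71, a = 0.33, b = 0.47 / 0.58 / 0.66: power 0.798 / 0.805 / 0.801.
- n = 53, a = 0.39, b = 0.59 (a pair inside the stated ranges): power 0.815.
- n = 53, a = 0.33: 0.67–0.72; a = 0.55: 0.90–0.97.

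The range is therefore plausible, but for a model whose IV varies.

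**2. The IV as named.** Let X be CFT group, with X = 1 for every completer. In the mediator regression M = i + aX + e, the slope is a = Σ(X − X̄)(M − M̄) / Σ(X − X̄)² = 0/0. The design matrix [1, X] has rank 1 of 2 at n = 53 and at n = 71. In the outcome regression Y = i + c′X + bM + e, the matrix [1, X, M] has rank 2 of 3. So a, the direct effect c′ and a×b are not identified. The slope of Y on M still is.

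**3. What a within-person model needs.** With time in place of X, a becomes the mean mediator change and b the slope of the outcome on that change. The product is then estimable, and the input that replaces the 0.33–0.55 is a mean change in SD units. The Sample Size section gives none. For the mean change alone (one-sample t test, two-sided 5%, 80% power), the normal approximation is (1.960 + 0.842)/√n:

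- n = 53: 2.802/7.280 = 0.385; with the t distribution, 0.392 SD.
- n = 71: 2.802/8.426 = 0.333; with the t distribution, 0.337 SD.

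**4. Power for a×b, as an illustration only.** The mean changes and the partial correlation of 0.30 are assumptions. The values 0.47 and 0.66 are the plan's unadjusted correlations taken as partial ones, which is optimistic. It is further assumed that the two mediator changes correlate 0.5, only the tested mediator affects the outcome, and baseline values are independent of mediator change (1,000 data sets, 1,000 resamples each).

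| Mean change | n = 53, partial r 0.30 / 0.47 / 0.66 | n = 71, partial r 0.30 / 0.47 / 0.66 |
|---|---|---|
| 0.20 SD | 24% / 37% / 36% | 35% / 43% / 43% |
| 0.35 SD | 49% / 73% / 75% | 67% / 85% / 85% |
| 0.50 SD | 60% / 91% / 96% | 74% / 97% / 99% |

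**5. What a means in one arm.** The observed mean change is the sum of any CFT effect and any change that would have happened anyway. Only the sum is estimated, so the interval for a×b excludes zero just as often when the whole mean change is drift.

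**The case against.** The strongest reply is that the Analysis sentence explains mediation in general terms and never says that a constant column will be entered in a regression. The principal question asks about mediating change in the group, the design is called within-group, measures are repeated, and the Analysis section says that change in mediators and outcomes will be measured. On this reading a within-person analysis is intended and only its details are missing.

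Much of that stands: a within-person model is the natural reading, and no one could run the literal one. But no section supplied names time as the IV, writes the paths, assigns waves to them, lists covariates or says which quantity and outcome the interval belongs to. The condition of association with the intervention is listed separately from change during it, and it has no test in one arm. The Sample Size section also argues from an intervention-mediator relation. The gap is therefore more than missing detail.

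A reader might infer three stronger things that the documents do not support:

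- *The study can answer nothing.* The mediator-outcome path, the pre-post changes and the secondary question ("Which is the better predictor of change - self-compassion or psychological flexibility") remain estimable.
- *53–71 is too small.* The power table rests on assumed mean changes. At 0.50 SD with the plan's own correlations, both sample sizes exceed 90%.
- *The choice to adjust for the week-5 outcome is shown to reverse the result.* That adjusted model asks about mediation after week 5. If mediation is complete by then, its true effect is zero by construction, so a disagreement between the models would reflect two questions, not two answers to one.

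**Conclusion.** The concern holds and should be settled before the data are analysed. With CFT group as the IV, the a path, the direct effect and a×b do not exist in this design, and the decision rule for the principal question cannot be applied. This follows from the document's own description of the cohort and needs no numerical assumption.

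The sample-size consequence is narrower: the stated basis does not match any model this design can fit, and the adequacy of 53–71 is unknown until a mean mediator change and a partial mediator-outcome correlation are assumed.

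The inability to separate CFT from natural drift or regression to the mean belongs to any single-arm design. Rewriting the model does not cure it, so it limits the conclusion, which the Analysis section currently words as explaining the intervention's influence.

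**What to change.** In the Analysis section, replace CFT group as the IV, and the condition of association with the intervention, with a within-person model fixed before analysis. One option, for each mediator and each named outcome:

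- a = mean mediator change from week 1 to week 5;
- b = coefficient of that change in a regression of the week-11 outcome on the week 1–5 changes in both mediators, adjusted for baseline outcome and both baseline mediators;
- a×b with a 95% bootstrap confidence interval, the level being stated.

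Check that the named software can bootstrap a mean times a coefficient. Examine sensitivity to clustering by delivery group. Groups are booked for at most 15, so 53–71 completers come from at least 4 or 5 groups (53/15 = 3.5; 71/15 = 4.7), and resampling individuals ignores this.

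Report the model that also adjusts for the week-5 outcome as a sensitivity analysis, labelled as addressing mediation after week 5. It is available for the HADS and SWEMWBS only, since Data Collection does not schedule the BPI-SF at week 5.

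Word the conclusion as early mediator change predicting, or statistically accounting for, outcome change during the programme. State that one arm cannot separate this from natural drift or regression to the mean.

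In the Sample Size section, give the power of 53–71 under an assumed mean mediator change and partial mediator-outcome correlation.

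**Cost.** No new measures or visits. The causal claim becomes weaker, and the sample-size text must be rewritten. This option does not use mediator change in weeks 5–11, and it does not settle the order of change within weeks 1–5.

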#### Recruitment

2-3 new Pain Management Programme groups start every month, each running for 11 weeks at the Astley Ainslie Hospital in Edinburgh. 6 groups run every week and each group is booked for a maximum of 15 people. These groups are run by at least two qualified members of the clinical team (Clinical Psychologists and Physiotherapists). There will be no need to advertise the research outwith normal clinical operations because clinical staff will offer all group participants the opportunity to participate in the research during their initial assessment, and data collection will overlap with existing routine outcome measures.

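### With everyone treated, no comparator and one pre-treatment score, the plan's mediation rule can be met by change over time alone; a positive result shows association during the programme, not an effect of the group

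*Combined protocol and SAP*

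**What the plan says.** The Design section states: "This study will follow a within-group (non-randomised) effectiveness-implementation design". Procedure fixes the measurement times. For the only occasion before treatment it says: "Those who can provide written informed consent will complete pre-group measures at the start of week 1". For the two later occasions the same section says: "Mid-group measures will be completed at the end of week 5 and post-group measures will be completed at the end of week 11". Data Collection repeats this schedule, with the week-5 occasion limited to the starred questionnaires. No control group, waiting period or second baseline is described.

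The week-1 score is not the first contact. People are identified at an initial assessment after referral. Those judged suitable "will be offered an introductory group session, followed by invitation to an upcoming 11-week group". Recruitment says: "clinical staff will offer all group participants the opportunity to participate in the research during their initial assessment, and data collection will overlap with existing" (the sentence goes on to name the service's routine measures). The interval from assessment to week 1 is not given.

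The Analysis section defines a mediator by three conditions: "a variable must change during the intervention, be associated with the intervention, and have an impact on the outcome". It names linear regression with a bias-corrected bootstrap in PROCESS, and takes an interval that excludes zero as evidence of mediation. Its hypothesis is worded causally: the mediators are to account for the group's effect on final outcome.

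**The concern.** Participants' scores may move between week 1 and week 11 for reasons unrelated to the group: the usual course after referral, repeated completion of the same forms, or the fading of a bad spell. If mediators and symptoms move together for such reasons, the plan has no element that would show it, and its decision rule would still report mediation.

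The conclusion is what is at stake. The Background faults an earlier self-compassion study because it could speak only to association, and the Rationale presents this study as the next step towards direction. For the question of whether the group caused the change, this design has a similar limit, but the Analysis section does not say so.

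**Working it through.** **Step 1. Hold the plan's conditions against the design.**

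- *Change during the intervention.* Any average movement between week 1 and week 11 satisfies this, whatever its cause.
- *Association with the intervention.* Everyone attends the group, so the independent variable is constant. Association with the group cannot be separated from elapsed time.
- *Impact on the outcome.* Mediator and outcome changes that correlate for any reason can satisfy this. Even a genuine effect of the mediator on symptoms would not show that the group moved the mediator.
- *Interval excludes zero.* This concerns sampling error and says nothing about the source of the change.

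The week-5 score helps with time order. It does not separate treatment from natural course.

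**Step 2. The plan's own figure.** The plan gives no figure for drift. Its only design figure is the sample size of 53-71 at 0.8 power, used here only as n. As a check, take joint power as the product over the two paths of Φ(atanh(r)·√(n−3−k) − 1.96), with k = 0 for path a and 1 for path b. The lowest quoted path-a correlation, 0.33, with path b at 0.47 to 0.66, needs n = 70-72, which agrees with 71. The lower end, 53, does not follow directly from the quoted correlations (0.55 with the same path-b values needs 26-38). The guideline table is not in the documents, so that end is left open. Nothing below depends on it.

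**Step 3. How often would the rule be met with no treatment effect?** Taken literally, a constant independent variable gives no estimable path, and the plan specifies no within-person form, so one is assumed.

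Inputs: n = 53 or 71 (Sample Size); bias-corrected bootstrap (Analysis). Assumed: 95% two-sided interval (the plan gives no level), equal drift d in mediator and outcome in SD units, correlation of changes 0.5, 11-week stability ρ of 0.6 or 0.8.

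Model:
- SD of change s = √(2(1−ρ)), which is √0.4 = 0.632 at ρ = 0.8 and √0.8 = 0.894 at ρ = 0.6.
- Mediator change = d + s·u and outcome change = d + s·v, with corr(u, v) = 0.5.
- Indirect effect = mean mediator change × slope of outcome change on mediator change. Its expected value is about d × 0.5, so d = 0.2 gives 0.10 SD labelled as mediated although the treatment does nothing.

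Each cell has 600 simulated studies with 600 resamples. The simulation error is at most √(0.5 × 0.5/600) = 0.020.

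Share of studies in which the interval excludes zero:

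| Drift d (SD) | n=53, ρ=0.8 | n=53, ρ=0.6 | n=71, ρ=0.8 | n=71, ρ=0.6 |
|---|---|---|---|---|
| 0 | 9.5% | 7.5% | 8.3% | 5.0% |
| 0.1 | 28.2% | 17.7% | 30.8% | 19.7% |
| 0.2 | 67.2% | 40.8% | 77.0% | 52.8% |
| 0.3 | 92.2% | 73.3% | 98.0% | 83.7% |

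The ranges are 5-10% at zero drift, 18-31% at 0.1 SD, 41-77% at 0.2 SD and 73-98% at 0.3 SD.

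**Step 4. Would subtracting a lead-in change repair this?** Let Y0, Y1 and Y2 be the scores at assessment, week 1 and week 11, and let k be the week 1-11 length divided by the lead-in length. The adjusted change is Y2 − Y1 − k(Y1 − Y0) = Y2 − (1+k)Y1 + kY0. With independent errors of equal variance, its error variance relative to simple change is (1 + (1+k)² + k²)/2. At k = 1 this is (1+4+1)/2 = 3; at k = 2 it is (1+9+4)/2 = 7. That is a heavy price at n = 53-71, and it relies on drift being linear.

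**The case against.** The design is declared openly as within-group and non-randomised, and the effectiveness label belongs to a cited design type. No test of effectiveness is specified. The Analysis section also speaks of measuring change over the course of the group, which is close to what the design can support. All of this stands, so the point is confined to how a positive result will be read.

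A reader might infer four stronger things, which the documents do not support.

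- *The single baseline is itself the defect.* The root cause is the missing comparator. With a concurrent control, one pre-treatment score would be enough.
- *Change alone declares mediation.* It is one of three joint conditions. The point holds because the other two give no protection either.
- *Regression to the mean can be calculated from the quoted retest figures.* Taking (1−r) × 1 SD with 0.94 (HADS), 0.83 (SWEMWBS) and 0.80 (self-compassion) gives shifts of 0.06, 0.17 and 0.20 SD, and a paired test could be powered on these. But nobody is selected on the week-1 score: the Participants section sets no score threshold, and selection happens at referral and assessment. If errors are independent between occasions, that regression is complete before week 1 and the expected later shift is zero. Only slow fluctuation leaves a remainder, and the documents give no figure for it. They also give no retest figure for psychological flexibility, and the plan contains no paired test of mediator change.
- *A lead-in score should be subtracted as a correction.* The interval may contain the introductory session, so it is not untreated; linear scaling is unsupported; and precision falls as shown in Step 4.

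**Conclusion.** The point holds as a limit on interpretation. With everyone treated, no comparator and one pre-treatment score, neither the three mediator conditions nor the interval rule can tell treatment change from change that would have happened anyway.

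The size is unknown and may be small. The 41-77% at 0.2 SD rests on the assumed drift, the assumed correlation of 0.5, the assumed stability and an assumed within-person model; at 0.1 SD the range is 18-31%. These figures show how readily the rule could mislead. They do not predict what will happen in this study, and they do not show that drift is present or that the group is without effect. The design cannot settle that in either direction, so the conclusion should be limited before the data are analysed.

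**What to change.** 1. In Analysis, replace the causal wording of the hypothesis with a statement such as: *A confidence interval that excludes zero will be taken to show that change in self-compassion or psychological flexibility is associated with change in symptoms during the programme. It will not be taken to show that the group caused either change.*
2. State that no effectiveness conclusion will be drawn from the within-group change. The cited design label in Design may stay.
3. Check whether the service already holds scores on the same questionnaires from the initial assessment or introductory session; the documents do not say. If it does, and consent covers their use, report the change from that point to week 1 descriptively as a check on drift, with the interval length, and do not subtract it. Information sheets and consent forms are issued at week 1, so cover for earlier scores has to be confirmed.

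Cost: two wording changes and a small descriptive table. The price is a weaker causal claim. No added visit or questionnaire is needed.
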